Cover Page

Title: Artificial Intelligence Screening for Body Dysmorphic Disorder in Aesthetic Surgery: Improving Patient Safety and Outcomes

• NCT Number: [NCT Number Here]

• **Document Date:** August 30, 2024

• **Document Review Statement:** This document was most recently updated and reviewed by the sole researcher, [name], EMBA, on August 30, 2024. As there is no human subjects protection review board required for this study, this date reflects the most recent review and update by the principal investigator.

Study Protocol

Introduction: This study protocol outlines the procedures, objectives, and methodologies for the observational study titled "Artificial Intelligence Screening for Body Dysmorphic Disorder in Aesthetic Surgery: Improving Patient Safety and Outcomes." The primary aim is to evaluate the clinical utility of an Al-powered screening tool for Body Dysmorphic Disorder (BDD) in patients seeking elective aesthetic surgery.

Study Objectives

- To evaluate the effectiveness of the Al-based screening tool in identifying patients at risk for BDD.
- To determine the correlation between various demographic and psychological factors (such as age, gender, and stress levels) and positive BDD screening results.
- To assess the impact of early psychological intervention on surgical decision-making and outcomes.

Study Design

This is an observational study with a prospective time perspective. The study involves the collection of clinical and psychological data from patients seeking elective aesthetic surgery. The AI model analyzes this data to provide risk scores and identify patients who may benefit from psychological intervention.

Participant Eligibility

Inclusion Criteria:

- Individuals aged 18 and older.
- Completion of the Body Dysmorphic Disorder Questionnaire (BDDQ).

Exclusion Criteria:

- Individuals below 18 years of age.
- Patients who did not complete the Body Dysmorphic Disorder Questionnaire (BDDQ).

Study Population Description

Participants are individuals seeking elective aesthetic surgery. They will complete the BDDQ and provide demographic and psychological data, including age, gender, and recent stress levels. The AI model will analyze this information to screen for BDD.

Data Collection: The following data will be collected from each participant:

- Age
- Gender
- Stress levels
- BDDQ scores
- Surgical outcomes (where applicable)
- Patient satisfaction (as measured by the Visual Analog Scale, VAS)

Study Procedures

Participants will undergo a screening assessment using the Al model, which evaluates multiple factors based on their responses to the BDDQ and additional psychological data. The Al model will generate risk scores and recommendations for psychological referral if necessary.

Follow-Up

The follow-up period for this study ranges from 1 to 43 months post-surgery, with a mean follow-up of 22 months. Data on patient satisfaction and surgical outcomes will be collected and analyzed.

Outcome Measures

Primary Outcome Measure

- Title: Patient Satisfaction Post-Surgery
- **Description:** The primary outcome measure is the level of patient satisfaction with the cosmetic surgery results, measured using the Visual Analog Scale (VAS) within the follow-up period after surgery.

Secondary Outcome Measure

- Title: Correlation Between Positive BDD Screening and Risk Factors
- Description: This measure evaluates the correlation between a positive Body Dysmorphic Disorder (BDD) screening result and various risk factors, including demographic factors (age, gender), psychological stress levels, and previous psychiatric history. The study will utilize chi-square tests to analyze gender differences in the prevalence of BDD among the patient population.

The goal is to identify patterns that could inform better patient selection and management in cosmetic surgery.

Conclusion

This study protocol provides a comprehensive overview of the study design, objectives, data collection methods, and outcome measures for the observational study "Artificial Intelligence Screening for Body Dysmorphic Disorder in Aesthetic Surgery: Improving Patient Safety and Outcomes." The integration of Al-powered screening is expected to improve patient selection, surgical planning, and overall outcomes in aesthetic surgery.

Statistical Analysis Plan (SAP)

Introduction: This Statistical Analysis Plan (SAP) outlines the statistical methods and analyses to be performed for the study titled "Artificial Intelligence Screening for Body Dysmorphic Disorder in Aesthetic Surgery: Improving Patient Safety and Outcomes." The primary aim of the study is to assess the effectiveness of the Al-powered screening tool in identifying patients at risk for BDD and its impact on surgical decision-making.

Study Objectives:

- To evaluate the effectiveness of the Al-based screening tool in identifying patients at risk for BDD.
- To determine the correlation between various demographic and psychological factors (such as age, gender, and stress levels) and positive BDD screening results.
- To assess the impact of early psychological intervention on surgical decision-making and outcomes.

Study Design: This is an observational study with a prospective time perspective. The study involves the collection of psychological and demographic data from patients seeking elective aesthetic surgery. The Al model analyzes this data to identify at-risk patients and provide recommendations for psychological evaluation.

Data Collection: The following data will be collected from each participant:

- Age
- Gender
- Stress levels
- BDDQ scores
- Surgical outcomes (where applicable)
- Patient satisfaction (as measured by the Visual Analog Scale, VAS)

Statistical Methods:

• Descriptive Statistics:

- Frequency and percentage of patients screening positive for BDD.
- Analysis of demographic data and stress factors.

Pearson Correlation:

o Correlation between BDD and factors such as age, gender, and stress.

Python code

```

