# Correlation calculations
stats.pearsonr(corr4['BDD'], corr4['Age'])
stats.pearsonr(corr4['BDD'], corr4['Stress in the last 3
months'])
stats.pearsonr(corr4['BDD'], corr4['Male'])
stats.pearsonr(corr4['BDD'], corr4['Female'])
```

• Chi-Square Analysis:

 Chi-square tests will be conducted to evaluate the differences in the prevalence of BDD between genders, helping to identify any statistically significant associations between gender and BDD.

Python code

```
from scipy.stats import chi2_contingency

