# Calculate the relative risk
relative_risk = (positive_BDD_male / positive_BDD_female) /
(negative_BDD_male / negative_BDD_female)
```

Outcome Analysis:

 Patient satisfaction levels as measured by the Visual Analog Scale (VAS).

Data Analysis:

Data analysis will be performed using Python in a Colab environment.
 The analysis will focus on correlations between BDD and identified risk factors, chi-square tests for gender differences, as well as the effectiveness of the AI model in screening for BDD.

Access Instructions: To request permission to access the individual participant data (IPD) and supporting information, please email [contact]. Detailed instructions for requesting access can be found at IPD Sharing Instructions.

Conclusion: This SAP provides a detailed plan for the statistical analysis of the study "Artificial Intelligence Screening for Body Dysmorphic Disorder in Aesthetic Surgery: Improving Patient Safety and Outcomes." The analysis aims to provide insights into the effectiveness of the AI model in identifying and managing patients at risk for BDD, ultimately improving surgical outcomes and patient safety.

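### The SAP promises an AI effectiveness result for BDD screening, but the only BDD measure collected is the questionnaire fed to the AI, and the AI is never compared with that questionnaire alone

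*Combined protocol and SAP*

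**What the plan says.** **What goes into the AI.** Under Study Population Description, the protocol says of participants: "They will complete the BDDQ and provide demographic and psychological data, including age, gender, and recent stress levels". It continues: "The AI model will analyze this information to screen for BDD". Study Procedures repeats the point, describing a model "which evaluates multiple factors based on their responses to the BDDQ and additional psychological data". Eligibility requires a completed BDDQ, so every participant has one.

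**What comes out.** The model is to "generate risk scores and recommendations for psychological referral if necessary".

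**What is recorded.** The Data Collection lists in the protocol and the SAP are the same: age, gender, stress levels, BDDQ scores, surgical outcomes where applicable, and VAS satisfaction. Neither list contains a diagnostic interview, a clinician's diagnosis, the result of a referral, or the AI score itself.

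**What is promised.** The first objective in both parts concerns the effectiveness of the AI "tool in identifying patients at risk for BDD". The SAP Introduction makes this the study's primary aim. SAP Data Analysis names correlations and chi-square tests as its focus, "as well as the effectiveness of the AI model in screening for BDD".

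**What is specified.** The SAP lists the frequency of positive screens, descriptive summaries of demographic and stress data, Pearson correlations of one `BDD` column with age, stress and gender (for example "stats.pearsonr(corr4['BDD'], corr4['Age"), a BDD-by-gender chi-square test, male-to-female ratios with a relative risk, and VAS satisfaction.

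**The concern.** A screening tool's effectiveness is its ability to separate people with the condition from people without it, judged by something other than the tool. Here the only available yardstick for BDD is part of the tool. Agreement between the two is partly built in, which is known as incorporation bias. It cannot show whether the AI improves on the questionnaire, leaves it unchanged or degrades it.

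A clinic that already uses the BDDQ needs to know whether adding the AI helps, and the plan contains no analysis of that. A report that follows the plan could credit the AI with performance that belongs to the BDDQ, on the aim that the SAP puts first.

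**Working it through.** **Step 1: set the text side by side.** The AI's inputs are the BDDQ plus age, gender, stress and other psychological data. The BDD measures recorded are the BDDQ only. The effectiveness analysis has no metric, no reference standard and no comparator. The `BDD` column has no stated source, which leaves two main readings:
- If it means BDDQ-positive, none of the specified analyses evaluates the AI.
- If it means AI-positive, its correlations with age, gender and stress relate the AI's output to its own inputs.

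**Step 2: is there a figure to reproduce?** No. The documents give no sample size, BDD prevalence, BDDQ accuracy, AI weighting or accuracy target. Everything below rests on assumptions.

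**Step 3: illustration with a continuous score.** Assumptions:
- True severity d is standard normal.
- BDDQ = 0.7d + noise, with variance 1.
- AI = √w × BDDQ + √(1−w) × E, where E is the other input, with variance 1.
- BDDQ-positive is the top 10% of BDDQ; truly affected is the top 5% of d.
- E is either pure noise or correlated 0.5 with d.

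Correlation with true severity at w = 0.8:
- BDDQ alone: 0.70.
- AI, E noise: √0.8 × 0.7 = 0.63, worse than the BDDQ.
- AI, E informative: (√0.8 × 0.7 + √0.2 × 0.5) / √(1 + 2 × 0.4 × 0.35) = 0.850 / 1.131 = 0.75, better than the BDDQ. Here 0.4 = √(0.8 × 0.2), and 0.35 = 0.7 × 0.5 is the BDDQ-E correlation.

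AUCs from 1,000,000 simulated subjects:

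| Score | AUC against BDDQ-positive | AUC against true status |
|---|---|---|
| BDDQ alone, or an AI that copies it | 1.00 | 0.89 |
| AI, w = 0.8, E noise | 0.96 | 0.86 |
| AI, w = 0.8, E informative | 0.97 | 0.92 |
| AI, w = 0.5, E noise | 0.88 | 0.79 |
| AI, w = 0.9, E noise | 0.98 | 0.88 |

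At w = 0.8 the middle column hardly separates a tool that degrades the BDDQ from one that improves it, and it ranks a plain copy above both.

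**Step 4: the same check with a yes/no rule.** Suppose the AI is positive when the BDDQ is positive or an extra factor is present. Assume BDDQ sensitivity and specificity of 60% and 70%, with the factor independent of the BDDQ given true status.
- Useful factor (40% of cases, 10% of non-cases): true sensitivity 1 − 0.4 × 0.6 = 76%; true specificity 0.7 × 0.9 = 63%.
- Noise factor (10% in both): true sensitivity 1 − 0.4 × 0.9 = 64%; true specificity 63%.

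Scored against the BDDQ, both rules have 100% sensitivity. Apparent specificity for the useful factor is (0.02 × 0.6 + 0.665 × 0.9) / 0.685 = 89% at 5% prevalence, and (0.06 × 0.6 + 0.595 × 0.9) / 0.655 = 87% at 15%. For the noise factor it is 90%. The useful rule therefore looks slightly worse than the useless one.

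**The case against.** **The SAP plans no sensitivity, specificity or AUC against the BDDQ, so the bias belongs to an analysis nobody has proposed.** The first half is right: the sponsor has not written a circular accuracy analysis, and a reader should not infer that one is planned. But an effectiveness result is promised, and for BDD status the listed data leave no other yardstick. The absence of a metric is part of the defect.

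**A reader might infer that agreement with the BDDQ is bound to look good.** That does not follow. In the noise case above, the AUC against the BDDQ falls to 0.80, 0.74 and 0.67 at weights of 30%, 20% and 10%, and the documents give no weight. Upward bias is expected; a flattering result is not certain.

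**A reader might infer that the AI is worse than the BDDQ.** The documents do not support that either. Nothing says the non-BDDQ inputs are uninformative, and with a moderately informative input the AI is the better tool.

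**VAS satisfaction is collected and is not named among the AI's inputs.** True, so it could give indirect evidence. It concerns surgical results, however, and so exists only in operated patients. Referral may influence who is operated on, and follow-up runs from 1 to 43 months. No planned analysis links VAS to the AI or the BDDQ. A gain in predicting satisfaction would not show better detection of BDD, and no gain would not show the reverse.

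**Conclusion.** The point stands in limited form. The plan names AI effectiveness in screening for BDD as its primary aim, collects no BDD measure independent of the AI's input, leaves the `BDD` column undefined, and specifies no comparison with the BDDQ alone. The conclusion rests on the text and does not depend on the simulation.

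The illustration shows only that an AUC of 0.96 to 0.97 against the BDDQ is compatible with a true AUC of 0.86 or 0.92, on either side of the BDDQ's 0.89. It depends on the assumed correlations, positivity rates and 80% weight, none of which is in the documents.

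A reader might also suppose that the missing comparison could be run on data already held for every participant. The documents do not establish this: the AI score is generated, but it is absent from both Data Collection lists and from the SAP code.

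**What to change.** 1. Add the AI risk score and an AI-positive flag, with the rule that defines it, to both Data Collection lists. Define the `BDD` column as either BDDQ-positive or AI-positive.
2. In SAP Data Analysis, state that the BDDQ is not a reference standard for the AI. Report no sensitivity, specificity or AUC against it. Report an AI-by-BDDQ cross-classification instead, with both discordant counts (AI-positive/BDDQ-negative and AI-negative/BDDQ-positive) and 95% confidence intervals for the corresponding proportions.
3. Limit the conclusion to how the AI reclassifies patients relative to the BDDQ. Withdraw the claim of effectiveness in identifying BDD, in the objectives as well as the conclusions, because no independent diagnosis is collected.
4. Label any model of VAS on BDDQ plus AI score as exploratory, in operated patients only, and as describing prediction of satisfaction rather than detection of BDD.

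**Cost.** Two extra variables, one extra table, some rewording, and a less favourable claim for the AI.

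Keeping the effectiveness claim would be a larger undertaking, since it needs an independent diagnosis. For example, estimating a sensitivity of 0.80 to within 10 points takes 1.96² × 0.8 × 0.2 / 0.1² ≈ 62 diagnosed patients. If everyone is verified, that means about 414 participants at an assumed prevalence of 15% (62 / 0.15) or 1,240 at 5% (62 / 0.05). Verifying only the referred patients would introduce verification bias.

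### The primary outcome, VAS satisfaction, has no rating time beyond a follow-up of 1 to 43 months, and no planned analysis relates it to the screening result or to time since surgery

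*Combined protocol and SAP*

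**What the plan says.** The Follow-Up section of the protocol states: "The follow-up period for this study ranges from 1 to 43 months post-surgery, with a mean follow-up of 22 months". It adds: "Data on patient satisfaction and surgical outcomes will be collected and analyzed". Under Primary Outcome Measure, satisfaction is "measured using the Visual Analog Scale (VAS) within the follow-up period after surgery". No visit, window or number of ratings is given.

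In the SAP, the whole entry under Outcome Analysis is "Patient satisfaction levels as measured by the Visual Analog Scale (VAS". The Data Analysis section then says "The analysis will focus on correlations between BDD and identified risk factors, chi-square tests for gender differences". The same sentence goes on to name the effectiveness of the AI model in screening for BDD, also without a method. Satisfaction is not mentioned there.

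The protocol Introduction says "The primary aim is to evaluate the clinical utility of" the AI screening tool. The SAP Introduction puts the aim as identifying at-risk patients and the tool's effect on surgical decision-making. One listed objective is "To assess the impact of early psychological intervention on surgical decision-making and outcomes". According to Study Procedures, the model will "generate risk scores and recommendations for psychological referral if necessary".

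**The concern.** A primary outcome needs a time at which it is measured and an analysis tied to the study's question. Here both are open. The secondary outcome has code for its tests, while the primary outcome does not have even a named summary statistic.

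Two things are at stake. First, a satisfaction summary that is never set against the screening result says nothing about whether the tool is useful. Second, if satisfaction changes with time since surgery, a pooled value depends on when patients happened to be rated, and the plan neither fixes nor reports that. With timing, method and comparison all unstated, each can be chosen after the data are seen.

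The plan also does not say how participants without surgery are handled. They can have no rating of a surgical result.

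**Working it through.** **1. The follow-up figures.** Inputs from Follow-Up: range 1 to 43 months, mean 22. The span is 43 − 1 = 42 months and the midpoint is (1 + 43)/2 = 22, so the stated mean is compatible with the range. It cannot be verified, because no sample size or distribution is given. These figures describe length of follow-up. The time of the VAS rating within follow-up is not stated.

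**2. What each SAP item uses.**

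| SAP item | Variables | VAS | Time since surgery |
|---|---|---|---|
| Descriptive Statistics | positive screens, demographics, stress | no | no |
| Pearson Correlation (four) | `BDD` with age, stress, male, female | no | no |
| Chi-Square Analysis | `BDD` by female | no | no |
| Gender ratios, relative risk | `BDD`, male, female | no | no |
| Outcome Analysis | VAS | named, no method | no |
| Data Analysis | risk-factor correlations, gender tests, AI effectiveness | no | no |

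No row joins VAS to `BDD`, to an AI score or to time.

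**3. Texts that come close.** The Follow-Up sentence promising analysis names no method. AI effectiveness concerns detection of BDD, not satisfaction. The objective on psychological intervention mentions outcomes but has no matching analysis.

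**4. Could mixed timing matter?** This is an illustration only. Assume a 0–10 scale and an early deficit in satisfaction of f(m) = 2·exp(−m/6) points at month m; neither is in the documents. The pooled deficit is then:

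*Only if VAS is rated at the end of follow-up* (rating times range 1–43, mean 22):
- nearly all near month 22: 2·exp(−22/6) = 0.05
- uniform over 1–43: 2·6·(e^(−1/6) − e^(−43/6))/42 = 0.24
- half at month 1, half at month 43: e^(−1/6) + e^(−43/6) = 0.85, the largest value under this condition

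*If VAS may be rated earlier:*
- follow-up uniform over 1–43 and each rating uniform between month 1 and the end of follow-up: mean rating time (1 + 22)/2 = 11.5 months, deficit 0.61
- everyone rated at month 1: 2·exp(−1/6) = 1.69

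If satisfaction is constant, timing has no effect. If it changes linearly, the pooled mean equals the value at the mean rating time, which is 22 months only if ratings are taken at the end of follow-up.

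**5. Precision cost of adjusting for months.** With proportion screen-positive p, a gap g between groups in mean months at rating, a within-group SD of s months, and no true change over time, the standard error is multiplied by √(1 + p(1 − p)g²/s²). Assume p = 0.15, so p(1 − p) = 0.1275:
- g = 12: s = 11 gives √(1 + 0.1275·144/121) = 1.07; s = 6 gives 1.23; s = 4 gives 1.47
- g = 6: 1.02, 1.06 and 1.13 for the same s
- g = 0: no loss

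The documents give none of p, g or s.

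**The case against.** The strongest reply is that no objective asks whether satisfaction differs by screening result among operated patients. On that view the regression adds a question instead of repairing one. This stands in part: the regression does not answer the decision-making or psychological-intervention objectives, and it mixes BDD risk with any effect of referral. But satisfaction is the plan's own primary outcome and utility of the tool is its own primary aim, and nothing in the plan connects the two.

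A second reply is that the sentence giving 1 to 43 months reads as a description of data, not as a rule for accepting ratings. That is fair. An exact mean suggests the figures may already be observed, and the plan should say so. Either way, no other time for the rating is given.

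Three stronger readings are tempting and not supported:
- *That timing biases a comparison of groups.* The plan compares no groups on VAS. A false difference, equal to slope times gap in mean rating time (for example an assumed 0.05 points per month × 12 months = 0.60), would arise only if groups were later compared without accounting for time.
- *That the screening result is absent from the code.* The 0/1 variable `BDD` is undefined and may be the BDDQ result or a dichotomised AI result. What can be said is that neither is related to VAS.
- *That surgery and rating dates are not collected.* The Data Collection lists omit them, but they also omit psychiatric history and the AI score, so they are not exhaustive. Follow-up expressed in months suggests dates may exist.

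**Conclusion.** The concern holds for the specification. The primary outcome has no rating time other than the follow-up period, and no planned analysis relates it to the screening result or to time since surgery. This can be verified line by line and rests on no assumption. As written, the primary outcome yields at most a pooled summary of ratings at mixed times in operated patients, which cannot inform the tool's clinical utility.

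The size of any timing effect is unknown and possibly zero. The illustrative deficits, from 0.05 to 1.69 points, depend wholly on an assumed scale, an assumed curve and assumed rating times. They show that the stated range and mean do not determine the pooled value, and they are not evidence that satisfaction changes. The gap concerns the primary outcome and should be closed, but numerical harm is not shown.

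**What to change.** In the SAP:

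1. State which VAS rating counts if there are several, and record months from surgery to that rating.
2. Define the screening-positive variable, and say whether `BDD` is the BDDQ or the AI result.
3. Analyse VAS by linear regression on screening result (positive versus negative) with months since surgery as a covariate. Report the difference with a 95% CI. Add a non-linear time term, such as log months, as a sensitivity analysis, since a linear term may not capture an early change.
4. Report how many screen-positive and screen-negative participants had no surgery and so no VAS.
5. Limit the conclusion to an association in operated patients, and state that it does not answer the decision-making or psychological-intervention objectives.
6. State whether the 1–43 month range and 22-month mean are planned or already observed. If observed, label the VAS analysis exploratory.

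The cost is SAP wording, dates of surgery and rating for each patient, a few counts and one regression with its sensitivity analysis. Some precision is lost if time since surgery differs between groups: about 2% to 47% on the standard error across the assumed 6- and 12-month gaps above, and almost nothing if timing is balanced. No worst case can be stated, because the within-group spread of rating times is not given.

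### The primary VAS outcome is defined only for operated patients, and no planned outcome or analysis covers the surgical decision that the tool is meant to influence

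*Combined protocol and SAP*

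**What the plan says.** - **Who is enrolled.** Under Participant Eligibility, the protocol asks for age 18 or over and a completed BDDQ. The Study Population Description adds: "Participants are individuals seeking elective aesthetic surgery". Having surgery is not a criterion.
- **What is measured.** Under Outcome Measures, "The primary outcome measure is the level of patient satisfaction with the cosmetic surgery results", and this is "measured using the Visual Analog Scale (VAS) within the follow-up period after surgery". The Follow-Up section also counts time from surgery: "The follow-up period for this study ranges from 1 to 43 months post-surgery, with a mean follow-up of 22 months".
- **What is collected.** The Data Collection lists in the protocol and the SAP contain the item "Surgical outcomes (where applicable". The next item, VAS satisfaction, carries no such qualifier, although both lists are introduced as applying to every participant.
- **What the tool does.** Under Study Procedures, the model "will generate risk scores and recommendations for psychological referral if necessary". No rule linking the result to whether surgery goes ahead is stated.
- **What it is meant to achieve.** The SAP Introduction includes in the primary aim "its impact on surgical decision-making". The protocol's Conclusion expects better selection of patients, and the third objective in both parts concerns the effect of early psychological intervention on surgical decisions and outcomes.
- **What is analysed.** The SAP's Outcome Analysis is one line naming VAS satisfaction levels. It gives no analysis set, comparator or rule for patients without surgery.

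**The concern.** The population at entry and the population with a primary outcome are not the same by definition. The step between them is the decision to operate, which the tool is intended to inform. Two consequences follow.

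First, a VAS mean in operated patients describes those patients only. If screening leads less-satisfied patients away from surgery, that mean is higher than it would otherwise have been even though nobody's own result has improved. A reader could then take selection for benefit.

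Second, avoiding surgery in someone likely to be dissatisfied may be exactly the benefit intended, yet the VAS cannot show it, because that person has no rating. The plan contains no other variable that would. Screening frequency, correlations with risk factors and the chi-square test by gender all describe who screens positive. None describes what was then decided.

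**Working it through.** The documents state no sample size, screening-positive rate, VAS range, VAS mean or share of patients operated on, so there is no planned figure to reproduce. The check has two parts.

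**1. Does the plan cover the decision to operate?** The Data Collection lists name age, gender, stress, BDDQ scores, surgical outcomes and VAS. None is a disposition variable (operated, deferred, not operated). The SAP's methods are descriptive statistics, Pearson correlations, a chi-square test with male-to-female ratios, and the VAS line. None uses disposition. The decision-making part of the aim therefore cannot be answered from the plan as written.

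**2. How far could selection alone move the VAS mean?** All inputs are assumptions:
- *p*: share screening positive
- *d*: share of screen-positives not operated on
- *G*: mean VAS after surgery in screen-negatives minus that in screen-positives, on a 0-10 scale
- all screen-negatives are operated on, and no individual's satisfaction changes

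Share of positives among operated patients: q = p(1 − d)/(1 − pd).

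Shift in the mean relative to operating on everyone: G(p − q) = G·p·d·(1 − p)/(1 − pd).

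Share of enrolled patients without a primary outcome: pd.

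Worked case with means of 8.5 (negative) and 5.5 (positive), so G = 3, and p = 0.15:
- d = 0: 0.85 × 8.5 + 0.15 × 5.5 = 8.05
- d = 0.5: q = 0.075/0.925 = 0.081; mean = 8.5 − 3 × 0.081 = 8.26, a shift of +0.21
- d = 1: mean = 8.50, a shift of +0.45

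The shift depends on the gap and not on the level of the means, so the gap is varied here:

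| p | d | No primary outcome (pd) | Shift, G = 0 | G = 1 | G = 3 | G = 5 |
|---|---|---|---|---|---|---|
| any | 0 | 0% | 0 | 0 | 0 | 0 |
| 15% | 50% | 7.5% | 0 | 0.07 | 0.21 | 0.34 |
| 15% | 100% | 15% | 0 | 0.15 | 0.45 | 0.75 |
| 25% | 50% | 12.5% | 0 | 0.11 | 0.32 | 0.54 |
| 25% | 100% | 25% | 0 | 0.25 | 0.75 | 1.25 |

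Over a wider grid (p from 5% to 30%, d from 25% to 100%, G from 1 to 5) the shift runs from 0.01 to 1.50 points. Patients who do not proceed for reasons unrelated to screening would add to the share without an outcome.

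**The case against.** The strongest reply is that the diversion is inferred. The only stated output of the tool is a risk score with a referral recommendation, and no passage says that surgery is deferred or declined. The statements about decisions and patient selection show intent and not occurrence. This stands, and it limits the point to a conditional one.

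The text can also be read as describing a cohort in which everyone was operated on: VAS is listed for all participants, and follow-up is given wholly in months after surgery. The follow-up range and mean look like realised figures, so for some patients surgery may have preceded scoring, in which case the tool could not have selected them. Against this, the design is called prospective, eligibility does not require surgery, and surgical outcomes are qualified as not always applicable. The documents leave the matter open. If all participants were operated on, the study could not observe an effect on the decision to operate.

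Third, the outcome's own title says that it is post-surgical, and such an outcome is legitimate in a descriptive study whose conclusion is limited accordingly. This also stands. No comparator is planned, so the VAS could not be attributed to screening even if every patient had surgery.

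A reader might go further and infer that the tool has in fact selected the primary population, that mean satisfaction will rise because of it, or that non-operated screen-positives vanish from the study. The documents support none of these. Diversion is not described; there is no reference period or group for a rise; and non-operated patients lack only the VAS, since nothing removes them from the screening, correlation or chi-square analyses. Nor does every effect on decisions fall among them, because surgical planning, which the protocol also mentions, concerns patients who are operated on.

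**Conclusion.** The point holds in conditional form. The primary VAS is defined only for operated patients within a wider enrolled population, and the plan does not say what a non-operated participant would rate. If referral changes who has surgery, the VAS mean is conditional on a decision influenced by the tool and cannot separate selection from benefit. Independently of whether that happens, the decision-making part of the SAP's primary aim has no outcome or analysis.

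The size is unknown. The shift is 0 if nobody is diverted or if the groups would be equally satisfied. With a 3-point gap and all screen-positives diverted it is about +0.45 at 15% positive and +0.75 at 25%, and it grows with the gap. Every input to these figures is an assumption. This should be fixed, with moderate confidence: the gap in definition and in outcomes is clear from the text, but whether a bias operates is not.

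**What to change.** 1. Record surgical disposition (operated, deferred, not operated) for every enrolled patient, and tabulate it by screening result. Report it beside the VAS, with the number operated and the number rated, each over the number enrolled. This is the main change: it supplies the missing outcome for the decision-making aim and shows whether any selection took place. A table showing that everyone was operated on would settle that question too.
2. Define the VAS analysis set as enrolled patients who had surgery, and align the Data Collection lists so that they no longer imply a rating from patients without surgery.
3. State in the SAP that the VAS mean in operated patients will not be interpreted as an effect of screening on satisfaction.

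Cost: one extra field per patient, one table and a few sentences of SAP text. The documents do not say from which source disposition would be taken, so the sponsor would need to name it. The downside is a narrower satisfaction claim. The table is descriptive: without a comparator it shows how decisions differ by screening result, and not what they would have been without the tool.
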